3.1.1.5 Follow-up period (Visit 10, week 20)

Patients will be followed up for 4 weeks after discontinuing investigational product. During this time patients can be treated for their type 2 diabetes according to country-specific or

regional guidelines as necessary without any further protocol restrictions. It is at the discretion of the investigator to continue with the metformin at the dosing schedule used during the double blind treatment period.

Table 3

Study Plan

| | Screening | Enrol ment | I I | | t period | | Follow- up visit | | | | |
|---|-------------|---------------|------|------|----------|------|---------------------|------|------|-------------------------|------|
| Visit | S | 1 (E) | 2 | 3 | 4 (R) | 5 | 6 | 7 | 8 | 9 (EoT) ^f | 10 |
| Week | -7 max | - 5 | -4 | -1 | 0 | 1 | 4 | 8 | 12 | 16 | 20 |
| Visit window (days) ^e | (-14 to -3) | (0) | (±3) | (±3) | (±3) | (±3) | (±3) | (±3) | (±3) | (±3) | (±3) |
| Screening informed consent and blood sample HgbA1c | X | | | | | | | | | | |
| Informed consent | | X | | | | | | | | | |
| Demography and medical history | | X | | | | | | | | | |
| Inclusion/Exclusion criteria | | X | X | X | X | | | | | | |
| Randomisation | | | | | X | | | | | | |
| Brief physical examination | | | X | X | | Х | X | Х | X | | Х |
| Complete physical examination | | Х | | | Х | | | | | X | |
| Vital signs | | X | Х | | X | Х | X | Х | Х | X | Х |
| Weight | | X | X | Х | X | Х | X | X | X | X | Х |
| Height | | X | | | | | | | | | |
| 12-lead ECG | | X | | | X | | | | | Х | |
| Concomitant medication | | X | X | Х | X | Х | X | Х | Х | Х | Х |
| Laboratory assessments ^a | | X | X | Х | X | Х | X | Х | Х | Х | Х |
| Pregnancy test ^b | | X | X | X | X | Х | X | X | X | X | Х |

| | Screening | Enrol ment | | | 16-week double blinded treatment period | | | | | | Follow- up visit |
|---|-------------|---------------|------|------|---|------|------|------|------|-------------------------|---------------------|
| Visit | S | 1 (E) | 2 | 3 | 4 (R) | 5 | 6 | 7 | 8 | 9 (EoT) ^f | 10 |
| Week | -7 max | - 5 | -4 | -1 | 0 | 1 | 4 | 8 | 12 | 16 | 20 |
| Visit window (days) ^e | (-14 to -3) | (0) | (±3) | (±3) | (±3) | (±3) | (±3) | (±3) | (±3) | (±3) | (±3) |
| AEs | | | X | X | X | Х | X | Х | X | X | Х |
| SAEs | | X | X | X | X | Х | X | X | X | X | Х |
| Dispense open label metformin | | | X | | X | | X | X | X | | |
| Dispense investigational product/placebo | | | X | | X | | Х | X | X | | |
| Drug accountability | | | | Х | Х | Х | X | Х | Х | X | |
| Diet and life-style advice | | X | X | Х | Х | Х | X | Х | Х | X | |
| Dispense glucometer at V2; provide supplies and instructions | | | X | Х | X | Х | X | X | Х | | |
| Dispense patient diary | | | X | X | X | Х | X | X | X | | |
| Patient diary review for/glucometer values/ hypoglycaemic events ^c | | | | Х | Х | Х | Х | Х | Х | Х | |
| Informed consent, blood sample for genetic research ^d | | | | | X | | | | | | |

a) Specifications of laboratory parameters will be shown in separate tables

b) Pregnancy test will be done on all female patients who are not postmenopausal or hysterectomised.

c) Patients should be instructed to contact investigator by phone if a hypoglycaemic event occurs, in cases specified in the patient diary.

d) Genetic informed consent must be obtained before genetic blood sample is taken. Blood sample donation is optional and can be done any time from Visit 4 (ie, randomisation) to Visit 9.

e) Once a patient is randomised, all visits should be scheduled relative to Visit 4. Any slippage in time from one visit must not accumulate to affect other visits.

f) EoT visit procedures should be performed in case if a patient is discontinued after randomisation, for any reason

3.2 Rationale for study design, doses and control groups

3.2.1 Study design and regulatory requirement

The current study is designed to demonstrate the efficacy and safety of dapagliflozin BID versus matching placebo BID in patients with T2DM who have inadequate glycaemic control on metformin alone.

Moreover, efficacy and safety of dapagliflozin QD co-administered with metformin will be compared with matching placebo QD co-administered with metformin.

The study has standard design features for a confirmatory pivotal Phase III FDC diabetes study (eg, multi-centre, randomised, double-blind, parallel group, co-administration of each of the active components, and placebo comparisons with the active add-on components) and incorporates the relevant features of the Committee for Proprietary Medicinal Products' guidance for investigations of diabetes (CPMP 2002) with regard to duration of treatment, choice of study population, and choice of outcome variables. The dapagliflozin 10 mg QD arm is a 'positive control with placebo', a measure of assay sensitivity, and not contributory to the primary objective and key secondary objectives.

3.2.2 Study doses and control groups

Investigational product doses

Dapagliflozin 2.5 mg and 5 mg tablets, administered orally BID and dapagliflozin 10 mg tablets administered orally QD with metformin, just prior to, or with, meals for the 16-week double-blind treatment period.

Control group

Matching placebo for dapagliflozin 2.5 mg and 5 mg tablets administered orally BID and matching placebo for dapagliflozin 10 mg tablet administered orally QD with metformin, just prior to, or with, meals for the 4-week placebo lead-in period and the 16-week double-blind treatment period.

Background therapy

Open-label metformin IR 500 mg tablets administered orally BID just prior to, or with meals, at doses \geq 1500 mg/day for the 4-week placebo lead in/open label metformin period and the 16-week double-blind treatment period. Metformin is approved for use at doses up to 3000 mg/day but this can differ between countries. In several countries, metformin is not indicated for use in patients with a creatinine clearance <60 ml/min because of metformin accumulation and an increased risk of lactic acidosis, a very rare condition that is associated with increased mortality. Metformin is contra-indicated for use in diseases which may cause sudden hypoxia such as dehydration, severe infection, respiratory failure, or a recent myocardial infarction. Efficacy, safety and tolerability of metformin are well documented in the literature.

Dapagliflozin

The results of pre-clinical pharmacokinetic and toxicology studies support the safety of conducting a Phase III clinical development program for dapagliflozin. In Phase I clinical pharmacology studies (single ascending-dose and 2-week multiple ascending-dose studies in healthy patients and patients with type 2 diabetes), dapagliflozin was safe and well tolerated with a favourable pharmacokinetic and pharmacodynamic profile. A Phase IIb study in patients with type 2 diabetes demonstrated good glycaemic efficacy and an acceptable safety profile over a wide range of doses. Based on considerations of efficacy, pharmacodynamic, and safety data from the Phase I and II programs, daily doses up to 10 mg daily of dapagliflozin have been chosen for the Phase III studies. Daily doses of 5 and 10 mg were chosen for this study as they have been extensively studied in Phase III trials. A recent publication has reported on the efficacy, tolerability and safety of dapagliflozin 2.5 mg, 5 mg and 10 mg once daily as add on therapy to metformin (Bailey 2010).

3.2.3 Choice of outcome variables

HbA1c is the variable of choice for assessment of glycaemic control and is required for registration purposes, but fasting plasma glucose will also be measured at each visit.

Because of its novel, complementary mechanism of action, dapagliflozin may have additive or synergistic HbA1c-lowering effects when given in combination with other antihyperglycaemic agents. Additionally, as beneficial effects on weight, systolic blood pressure (SBP) and FPG have been observed in other dapagliflozin studies, these variables have been chosen as key and non-key secondary objectives (see Table 4).

| Efficacy variable | Related objective | Rationale |
|-------------------|--|--|
| HbA1c | Change in HbA1c from baseline at week 16. Proportion of patients with HbA1c <7.0% at 16 weeks, in patients who had HbA1c ≥7.0% at baseline. | HbA1c is the clinical and regulatory parameter used to estimate glycaemic efficacy in patients with type 2 diabetes (CPMP 2002). HbA1c targets for patients with type 2 diabetes range from <6.5% (IDF 2005, AACE 2007) to <7.0% (ADA 2009, ADA 2010). The degree of change in HbA1c in patients with type 2 diabetes is related to the baseline HbA1c level; patients with higher HbA1c at baseline tend to have greater reductions in HbA1c when treated with any antihyperglycaemic agent (Bailey 2010, Bloomgarden 2006) |

Table 4Efficacy variables with related objectives and rationale

| Efficacy variable | Related objective | Rationale |
|------------------------|--|--|
| Fasting Plasma Glucose | Change in FPG from baseline at week 1. Change in FPG from baseline at week 16. | Fasting plasma glucose is a well-established measure of glycaemic efficacy, and is considered by the CHMP (Committee for Medicinal Products for Human Use) to be acceptable as secondary endpoint (CPMP 2002). |
| Weight | Percent change in body weight from baseline at week 16. Change in body weight from baseline at week 16. | More than 85% of patients with T2DM are overweight (BMI $\geq 25 \text{ kg/m}^2$) or obese (BMI $\geq 30 \text{ kg/m}^2$) (CDC 2004). Weight loss is a fundamental goal for the majority of patients with type 2 diabetes since it has been shown to improve comorbid conditions such as hypertension, dyslipidemia, heart disease, osteoarthritis, and sleep apnea |
| Blood pressure | Change in seated SBP and DBP from baseline at week 16 Proportion of patients with seated systolic blood pressure <130 mmHg, at week 16 who had seated systolic blood pressure \geq 130 mmHg at baseline | The American Diabetes Association and the Joint National Committee on Prevention, Detection, Evaluation and Treatment of High Blood Pressure (JNC 2004) guidelines recommend a blood pressure target of <130/80 in patients with diabetes (ADA 2009, JNC 2004). Lowering blood pressure in patients with diabetes has been shown to reduce the risk of coronary heart disease events, stroke, retinopathy and nephropathy (JNC 2004). |

Age

The prevalence of type 2 diabetes increases with age; it is therefore important to assess the safety of antihyperglycaemic agents in elderly patients. In this study upper age limit for patients is 77 years, taking into account the upper age limit based on local metformin prescribing guidelines, as well as the upper age limit used in a phase III dapagliflozin monotherapy study.

HbA1c

The HbA1c inclusion criterion at randomisation was selected to include patients with a wide range of glycaemic control. The lower bound of this HbA1c inclusion window (ie, 6.5%) reflects the most recent treatment guidelines (IDF 2005, AACE 2007) as well as the HbA1c threshold (6.5%) to diagnose T2DM (ADA 2010). Other guidelines recommend treatment to somewhat higher HbA1c targets such as HbA1c <7.0% (ADA 2009). Results of recent studies suggest that a rigorous lowering of HbA1c to stricter targets may not be appropriate for all patients, suggesting that the pathophysiology of type 2 diabetes needs to be considered in pharmacological treatment combinations (ACCORD 2008, ADA 2009, Hanefeld and Forst, 2010). The upper limit of the HbA1c inclusion window (ie, 10.0%) was chosen because insulin is generally the treatment of choice for patients with HbA1c values above this level (ADA 2009). The HbA1c inclusion window allows the evaluation of dapagliflozin coadministered with metformin versus placebo co-administered with metformin over a wide range of HbA1c. To ensure that dapagliflozin's and metformin's efficacy, safety and tolerability are studied over the entire range of HbA1c, patients will be stratified according to their HbA1c at randomisation, limiting the number of patients in Stratum 1 (HbA1c <7.0%) at randomisation to 20% of the total study population (see Section 3.1.1.4).

Kidney Function

The exclusion criteria that relate to creatinine and creatinine clearance are consistent with prescribing guidelines for metformin \geq 1500 mg/day.

Pregnancy or breastfeeding

Dapagliflozin has not been tested in pregnant women and the risks to embryo, foetus, and infant are unknown. For this reason, women who are pregnant or breastfeeding are excluded and women of childbearing age are instructed to take precautions to avoid becoming pregnant during the study.

Other

The purpose of the majority of the inclusion and exclusion criteria is to limit confounding factors that may complicate the interpretation of the study results (eg, corticosteroid-induced T2DM, haemoglobinopathies that would interfere with the HbA1c analyses) or to exclude patients whose safety could be compromised by participation in the study.

4. SUBJECT SELECTION CRITERIA

Patient population should be selected without bias.

Investigator(s) must keep a record of patients who entered pre-trial screening but were never enrolled eg, patient screening log.

Each patient should meet all of the inclusion criteria and none of the exclusion criteria for this study. Under no circumstances can there be exceptions to this rule.

4.1 Inclusion criteria

The following criteria apply to the enrolment (Visit 1), whereas inclusion criterion no. 6 applies to Visit 3 and Visit 4 (Randomisation).

- 1. Provision of informed consent prior to any study specific procedures
- 2. Diagnosis of T2DM
- 3. Men or women age ≥ 18 to ≤ 77 years old at time of consenting
- 4. Current antihyperglycaemic treatment with metformin immediate release formulation monotherapy ≥1500mg/day at a stable dose for at least 10 weeks prior to enrolment. Other treatment with OADs within the 10 weeks prior to enrolment is not permitted.
- 5. HbA1c \geq 6.7% and \leq 10.5%, based on central laboratory values from Screening Visit, and Enrolment Visit 1. Note 1: In the case that Stratum 1 has met its goal for randomised patients, communication will be sent out to all sites that screening and enrollment will only continue for patients in Stratum 2 with an HbA1c \geq 7.2% and \leq 10.5%. For these patients in Stratum 2, randomisation criteria of HbA1c \geq 7.0% and \leq 10.0% will apply (see also inclusion criterion no. 6, Note 2, below).
- 6. HbA1c $\geq 6.5\%$ and $\leq 10.0\%$, based on central laboratory values obtained at Visit 3, one week prior to randomisation. Note 2: In the case that Stratum 1 has met its goal for randomised patients, HbA1c randomisation criteria will change to those applicable for Stratum 2: HbA1c $\geq 7.0\%$ and $\leq 10.0\%$, based on central lab values at Visit 3, one week prior to randomisation.
- 7. Women of childbearing potential (WOCBP) who comply with the following:
 - Use a highly effective method of birth control (see below) to avoid pregnancy throughout the study and for up to 4 weeks after the study
 - Have a negative urine pregnancy test (minimum sensitivity 25 IU/L or equivalent units of HCG) within 72 hours prior to the start of study medication and at each visit

Definitions:

Women of Child Bearing Potential - Women between menarche and menopause who have not been permanently or surgically sterilized and are capable of procreation.

Women NOT of Childbearing Potential - Women who are permanently or surgically sterilized or postmenopausal. Permanent sterilisation includes hysterectomy and/or bilateral oophorectomy and/or bilateral salpingectomy but excludes bilateral tubal occlusion. Tubal occlusion is considered a highly effective method of birth control but does not absolutely exclude possibility of pregnancy. (The term occlusion refers to both occluding and ligating techniques that do not physically remove the oviducts).

Post Menopausal Women - Women will be considered postmenopausal if they are amenorrheic for 12 months without an alternative medical cause. The following age-specific requirements apply:

- Women under 50 years old would be considered postmenopausal if they have been amenorrheic for 12 months or more following cessation of exogenous hormonal treatments and have FSH levels ≥40 mIU/mL.
- Women over 50 years of age would be considered postmenopausal if they have been amenorrheic for 12 months or more following cessation of all exogenous hormonal treatments.

Highly effective method of birth control is defined as one that results in a low failure rate (eg, less than 1 percent per year) when used consistently and correctly. The following are considered acceptable methods of contraception: Total sexual abstinence; Vasectomised sexual partner; Tubal occlusion (ligation); IUD; IUS levonorgestrel Intra Uterine System (eg, Mirina); Etonogestrel implants (eg, Implanon, Norplan); Normal and low dose combined oral contraceptive pills; Norelgestromin/EE transdermal system; Intravaginal device (eg, EE and etonogestrel); Cerazette (desogestrel)

4.2 Exclusion criteria

Patients must not enter the study if any of the following exclusion criteria are fulfilled.

The following criteria apply to enrolment (Visit 1).

Laboratory value criteria apply at the start of placebo lead in/ open label metformin treatment period (Visit 2, using laboratory values from Visit 1).

Laboratory value criterion no. 27 should be repeatedly checked including at Randomisation (Visit 4, using laboratory value from Visit 3).

Endocrine and metabolic disorders

- 1. Diagnosis of Type 1 diabetes mellitus, known diagnosis of Maturity Onset Diabetes of the Young (MODY) or secondary causes of diabetes mellitus
- 2. History of diabetic ketoacidosis

- 3. Symptoms of poorly controlled diabetes including, but not limited to, marked polyuria, polydipsia, and/or greater than 10% weight loss during the 3 months prior to enrolment
- 4. FPG >270 mg/dL (>15.0 mmol/L)
- 5. BMI >45 kg/m²
- 6. History of bariatric surgery (ie, any surgery to treat obesity; for example, gastric banding or procedures that involve bypassing or transposing sections of the small intestine). History of liposuction is allowed.
- 7. Diabetes insipidus
- 8. Thyroid-stimulating hormone (TSH) and free T4 values outside normal range. An abnormal TSH value needs to be followed up with a free T4 test. Patients with abnormal free T4 values will be excluded. Patients with an elevated TSH and normal free T4 will be allowed if referred to their family doctor for thyroid hormone replacement therapy prior to randomisation.

Kidney disorders

- 9. Creatinine Clearance: <60 mL/min (calculated by Cockcroft-Gault formula) or a measured serum creatinine value of \geq 1.5 mg/dL (133 µmol/L) for male patients and \geq 1.4 mg/dL (124 µmol/L) for female patients
- 10. Urine albumine: creatinine ratio >1800 mg/g
- 11. History of unstable or rapidly progressing kidney disease
- 12. Known condition of familial renal glucosuria

Hepatic disorders

- 13. Severe hepatic insufficiency and/or significant abnormal liver function defined as aspartate aminotransferase (AST) >3X upper limit of normal (ULN) and/or alanine aminotransferase (ALT) >3XULN
- 14. Total bilirubin (TB) >2.0 mg/dL ($>34.2 \mu \text{mol/L}$)
- 15. Positive serologic evidence of current infectious liver disease including Hepatitis B viral antibody IgM, Hepatitis B surface antigen and Hepatitis C virus antibody
- 16. History of drug-induced liver enzyme elevations
- 17. History of severe hepatobiliary disease or hepatotoxicity with any medication

Cardiovascular disorders

- 18. Congestive heart failure defined as New York Heart Association (NYHA) class III or IV (see Appendix D), unstable or acute congestive heart failure. Note: eligible patients with congestive heart failure, especially those who are on diuretic therapy, should have careful monitoring of their volume status throughout the study.
- 19. Significant cardiovascular history within the past 3 months prior to the screening visit, defined as: myocardial infarction, unstable angina pectoris, transient ischemic attack, unstable or previously undiagnosed arrhythmia, cardiac surgery or revascularization (coronary angioplasty or bypass grafts), or cerebrovascular accident. In addition, patients who have unstable cardiovascular disease at enrolment in the judgment of the investigator are excluded from the study.
- 20. Blood pressure:
 - *At enrolment (Visit 1):* Systolic BP ≥170 mmHg and/or diastolic BP ≥110 mmHg
 - *At randomisation (Visit 4):* Systolic BP ≥160 mmHg and/or diastolic BP ≥100 mmHg

Hematologic/oncologic disorders/conditions

- 21. Haemoglobin ≤ 10 g/dL (≤ 100 g/L) for men; haemoglobin ≤ 9.0 g/dL (≤ 90 g/L) for women
- 22. History of chronic haemolytic anaemia or haemoglobinopathies (for example, sickle cell anaemia, thalassemia, sideroblastic anaemia)
- 23. Iron deficiency anaemia with iron therapy started in the past 12 weeks prior to enrolment visit, or a recent diagnosis of iron deficiency anaemia that requires therapeutic management within the next 6 months in the judgement of the investigator
- 24. Donation or transfusion of blood, plasma, or platelets within the past 3 months prior to Visit 1
- 25. History of malignancy within the last 5 years, excluding successful treatment of basal or squamous cell skin carcinoma or in situ carcinoma of the cervix.

Infectious disease/immunologic disorders

26. Known immunocompromised status, including patients who have undergone organ transplantation

Clinical Study Protocol Drug Substance dapagliflozin Study Code D1691C00003 Edition Number 1 Date 23 July 2010

Musculoskeletal disorders

- 27. Creatine Kinase (CK) >3xULN
- 28. History of drug-induced myopathy or drug-induced CK elevation

Reproductive status

29. Pregnant or breastfeeding patients

Prohibited medications

- 30. Use of antihyperglycaemic medications other than metformin during the 10 weeks prior to enrolment
- 31. Use of insulin within 24 weeks of enrolment (with the exception of insulin use during a hospitalization or during pregnancy in patients with past history of gestational diabetes).
- 32. Use of weight loss medication, including but not limited to sibutramine, phentermine, orlistat, rimonabant, benzphetamine, diethylproprion, methamphetamine, and/or phendimetrazine, within 60 days prior to enrolment.
- 33. Treatment with glucocorticoids equivalent to oral prednisolone ≥ 10 mg (betametasone ≥ 1.2 mg, dexamethasone ≥ 1.5 mg, hydrocortisone ≥ 40 mg) per day within 30 days prior to enrolment; topical or inhaled corticosteroids are allowed
- 34. Treatment with unstable doses of teriparatide, bisphosphonates and/or calcitonin (note: teriparatide, bisphosphonates and calcitonin are allowed provided the dose has not changed within 30 days prior to enrolment).
- 35. Treatment for Human Immunodeficiency Virus (HIV) and/or use of antiviral drugs (delavirdine, indinavir, nelfinavir, ritonavir, saquinavir).

Other

- 36. Intolerance, contraindication or potential allergy or hypersensitivity to metformin, placebo, or formulation excipients
- 37. Any clinically significant abnormality identified on physical examination, ECG or laboratory tests, which in the judgement of the investigator would compromise the patient's safety or successful participation in the clinical study
- 38. Patients who, in the judgement of the investigator, may be at risk for dehydration

- 39. Acute or chronic metabolic acidosis
- 40. History of alcohol abuse or illegal drug use within the past 12 months
- 41. Involvement in the planning and conduct of the study (applies to both AstraZeneca and Bristol-Myers Squibb staff or staff at the study centre)
- 42. Previous screening, enrolment or randomisation to treatment in the present study
- 43. Previous participation in a clinical study with dapagliflozin (BMS-512148) and/or with any other SGLT2 inhibitor in which the patient received at least one dose of investigational product
- 44. Participation in another clinical study during the last 1 month

For the participation in the optional genetic research, patients must not have had:

- 45. Previous bone marrow transplant
- 46. Whole blood transfusion within 120 days of the date of genetic sample collection

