3.1.1.2 Enrolment Visit (Visit 1, week –5)

Eligible patients should be seen for Visit 1 within 3 to 14 days after screening. Patients will sign informed consent, undergo repeated check for all applicable inclusion and exclusion criteria, and submit laboratory samples. Diet and lifestyle advice will be given.

The existing patient's metformin medication and dose will remain unchanged. No other antidiabetic drugs are allowed. If applicable, anti-hypertensive medication need to be reviewed and can be adjusted.

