During the placebo lead-in period, background antihypertensive medications should be adjusted in patients with seated systolic BP \geq 160 mmHg or seated diastolic BP \geq 100 mmHg. Only those patients with seated systolic BP <160 mmHg and diastolic BP <100 mmHg at the end of placebo lead-in period will be randomised.

At Visit 3 assessments are performed primarily to check eligibility for randomisation, following one week later. HbA1c, FPG and CK measured by the central laboratory in a sample taken at Visit 3 will be used for assessment of corresponding eligibility criteria at randomisation.

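### Renal eligibility (exclusion criterion 9) is not re-checked before randomisation: at first dose it rests on a Visit 1 creatinine about 35 days old

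*Protocol*

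**What the plan says.** Section 4.2 of the protocol sets the timing of the laboratory exclusion criteria: "Laboratory value criteria apply at the start of placebo lead in/ open label metformin treatment period (Visit 2, using laboratory values from Visit 1". It names one exception: "Laboratory value criterion no. 27 should be repeatedly checked including at Randomisation (Visit 4, using laboratory value from Visit 3". Criterion 27 is the CK limit. The renal limit, criterion 9, begins "Creatinine Clearance: <60 mL/min (calculated by Cockcroft-Gault formula" and adds sex-specific serum creatinine limits. It is not among the criteria to be repeated.

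Section 3.1.1.3 agrees on creatinine. It lists what is re-used at randomisation: "HbA1c, FPG and CK measured by the central laboratory in a sample taken at Visit 3 will be used for assessment". Table 8 (Section 6.4.6) marks serum creatinine, calculated clearance and electrolytes at Visit 1 and Visits 4 to 10, and leaves Visits 2 and 3 blank.

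Between Visit 1 and randomisation, blood pressure treatment can change. Section 3.1.1.2 says of Visit 1 that "anti-hypertensive medication need to be reviewed and can be adjusted". Section 3.1.1.3 says that in the lead-in "background antihypertensive medications should be adjusted in patients with seated systolic BP" at or above 160 mmHg, or diastolic at or above 100 mmHg. Neither section excepts diuretics.

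**The concern.** Section 3.1 gives as one aim of the lead-in that patients reaching randomisation should still satisfy the entry criteria. For CK, HbA1c and FPG, a Visit 3 result supports that. For renal function nothing does: the last value required before the first dose is the one from Visit 1.

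The interval is not inert. Antihypertensives may be changed in it, and Section 6.4.11 itself warns that combining diuretics raises renal, volume and electrolyte risk and notes that dapagliflozin has a modest diuretic effect. Section 3.2.3 ties the renal criterion to metformin prescribing, and metformin continues in all four arms.

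A patient whose clearance has drifted below 60 mL/min by week 0 can therefore be randomised and dosed, and then be found, after a confirmatory repeat, to meet discontinuation criterion 13 (Section 4.3.1). The stake is short, avoidable exposure and an avoidable early withdrawal in a few patients. The effect on the primary HbA1c analysis is negligible.

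**Working it through.** **Age of the value at first dose.** Table 3 puts Visit 1 at week -5, Visit 3 at week -1 and Visit 4 at week 0 (±3 days).

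- Visit 1 to Visit 4: 5 × 7 = 35 days; with the Visit 4 window, 35 - 3 = 32 to 35 + 3 = 38 days.
- Visit 3 to Visit 4: nominally 7 days. This is the age of the HbA1c, FPG and CK values.
- Creatinine draws strictly between Visits 1 and 4 in Table 8: none.

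**Why the Visit 4 sample does not close the gap.** Section 5.1 has the morning dose held until after the visit, so the sample is pre-dose. The drug is then taken with the first meal of that day. Section 6.4.6 allows 72 hours for results. No section shown makes randomisation or the first dose wait for them.

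**Whether a tube exists at Visit 3.** Table 9 plans 9 clinical chemistry samples of 8.5 mL: 9 × 8.5 = 76.5 mL, as stated. Table 8 has full chemistry at Visits 1 and 4 to 10, which is 8 visits. CK is also marked at Visit 3, so 8 + 1 = 9. The count matches only if a chemistry tube is drawn at Visit 3. This is an inference from the count, not a statement in the protocol.

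**Size, on assumed inputs.** The protocol gives no clearance distribution, so these inputs are assumptions: true clearance Normal with mean 100, 110 or 120 mL/min and SD 25 or 35; independent readings with within-person CV of 5, 8 or 10%; no true change in the lead-in; patients kept if the Visit 1 reading is at least 60. The simulation used 4 million draws per combination, scaled to 392 patients.

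| | Range | Of 392 |
|---|---|---|
| Current plan: Visit 4 reading <60 | 0.16-2.51% | 0.6-9.8 |
| Current plan: Visit 4 and repeat both <60 | 0.07-1.01% | 0.3-4.0 |
| Single Visit 3 reading: excluded | 0.16-2.52% | 0.6-9.9 |
| Visit 3 reading plus repeat: excluded | 0.07-1.01% | 0.3-4.0 |

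- Confirmed post-dose cases averted: 51-61% with a single reading, 31-43% with a repeat. The upper bounds are 4.0 × 0.61 = 2.4 and 4.0 × 0.43 = 1.7 patients.
- Of those excluded at Visit 3, the share with true clearance of 60 or more is 57-77% with a single reading and 32-49% with a repeat.
- A less favourable case, also assumed: if 10-20% of patients lose 10-15% of true clearance in the lead-in, 0.5-7.7 of 392 are confirmed below 60 after dosing, and a single Visit 3 reading averts 55-81%.

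**Room for a repeat.** A Visit 3 result within 3 days leaves 7 - 3 = 4 days. A repeat reported within another 3 days leaves 4 - 3 = 1 day. That is tight but feasible, and the Visit 4 window adds up to 3 days.

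**The case against.** The strongest reply is that nothing here is an error. Section 4.2, Section 3.1.1.3 and Table 8 agree on when creatinine applies, and the sentence in Section 3.1 states an aim; the operative rules are in Sections 4.1 and 4.2. That stands: this is a design choice that serves the stated aim poorly, not a contradiction that invalidates anything.

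A second reply is that the harm is already bounded. Note a to Table 8 has metformin withheld and creatinine repeated within a week on a first clearance below 60 mL/min, and the Visit 4 result can trigger this within 72 hours. Chemistry is drawn again at week 1, and criterion 13 follows on confirmation. Section 6.4.11 also asks for careful monitoring in patients on loop diuretics. This stands, and it is why the point is minor.

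A third reply is that the base-case numbers describe measurement variation around 60 rather than deterioration, and that many patients excluded by a re-check would truly qualify. That also stands, and it is the reason for allowing a repeat.

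Two stronger readings are tempting but unsupported. A reader might infer that creatinine and electrolytes are not sampled again before the first dose; the Visit 4 sample is pre-dose, and only its result is late. A reader might also infer that electrolyte eligibility goes stale in the same way. No exclusion criterion sets an electrolyte limit. Electrolytes enter through judgement, chiefly criterion 37 ("Any clinically significant abnormality identified on physical examination, ECG or laboratory tests"), while dehydration risk has its own criterion 38 ("Patients who, in the judgement of the investigator, may be at risk for dehydration"), and Section 5.2 continues eligibility review up to Visit 4. A sodium bar at 125 mmol/L would be a new criterion.

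**Conclusion.** The point holds for renal function. Criterion 9 is applied once, on a Visit 1 value that is 35 days old (32 to 38) at the first dose, and no newer creatinine result has to be seen before dosing. This fits poorly with the lead-in's stated aim, given that blood pressure treatment may be altered meanwhile.

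The grade is minor: a cheap patient-safety improvement. Under the assumed distributions with no true change, 0 to 4 of 392 patients would be confirmed below 60 mL/min after dosing, and a Visit 3 check would spare about two of them at most. The timing rests on the protocol's own schedule; the patient counts rest wholly on the assumed clearance mean, SD and CV. Appendices F, G and I (hyponatraemia, decreased renal function, visit guide) are not shown, and a pre-randomisation check could appear there.

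**What to change.** Add serum creatinine with calculated clearance to Visit 3 in Table 8, run on the chemistry sample that Table 9's count implies is already drawn. State in Section 4.2 that criterion 9, like criterion 27, is re-checked at randomisation on the Visit 3 value, with one repeat allowed before exclusion. Add creatinine to the list of Visit 3 results in Section 3.1.1.3. Electrolytes may be run on the same tube for the investigator's review under criterion 37, without a new sodium exclusion limit.

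Cost: a few added assays, no extra scheduled draw (the total stays at 9 × 8.5 = 76.5 mL), and an unscheduled repeat for the 1 to 10 of 392 patients whose first reading falls below 60 on the assumed inputs. With the repeat, about 0 to 4 of 392 more patients fail before randomisation, 32-49% of them with true clearance of 60 or more. Acting on a single reading averts more cases (51-61% rather than 31-43%) but excludes 1 to 10, of whom 57-77% truly qualify. The repeat is the better balance, given the safeguards already in place after dosing.
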